### 7.2.2 Uptake irreversibility/reversibility

Kinetics of F-rhPSMA-7.3 uptake in PCa lesions is compared to the availability of parent F-rhPSMA-7.3 in plasma by plotting SUVR of lesion and parent F-rhPSMA-7.3 in plasma, and by irreversible and reversible multiple-time graphical analyses (Patlak and Logan plots) (Logan, 2000).

### 7.2.3 Lesion detectability

Comparison of SUV in detected lesion(s) against pathology grading. Details of the planned histopathological analysis and the PSMA immunochemistry procedure are given in a separate Histopathology and Immunohistochemistry Manual prepared for this study.

## 7.3 Assessment of safety

### 7.3.1 Clinical safety assessments

A standard physical examination will be performed by the Investigator at the screening visit, and brief physical examinations will be performed before IMP administration and at discharge

from the site. The following organ systems will be checked: head, eyes, ears, nose, throat, cardiovascular, respiratory, musculoskeletal, gastrointestinal, hepatic, psyche, endocrine, dermatologic and lymph nodes.

A 12-lead ECG will be recorded at the screening visit. During the IMP administration visit, 12-lead ECG will be recorded at baseline (between -120 to -15 min), 5 min pre-injection and at 90, 180 and 250 min after IMP administration (healthy volunteer subjects) or at the baseline, 5 min pre-injection, 45 min, 120 min, 180 min and 240 min after IMP administration (subjects with PCa). Continuous 2-lead ECG monitoring will be performed from 5 min pre-injection until the end of the PET scan visit.

Vital signs (body temperature, respiration rate, supine systolic and diastolic BP and HR) will be measured after 5 min rest at the screening visit. During the IMP administration visit, vital signs will be measured at baseline, 5 min pre-injection and 2, 5, 10, 15, 30, 60, 90, 180 and 250 min post-injection (healthy volunteer subjects) or at baseline, 5 min pre-dose and 5, 10, 15, 30, 45 120, 180 and 240 min post-injection (subjects with PCa). The injection site will also be monitored for signs of any adverse effects.

At 24 ( $\pm$  6) hr after IMP administration, AEs, concomitant medications, 12 lead ECG and vital signs (body temperature, respiration rate, supine systolic and diastolic BP and HR) will be recorded and blood and urine samples will be collected for safety evaluations. The injection site will be examined and any bruising or erythema will be recorded as an AE.

Additional safety data (physical examination findings, 12-lead ECG and vital signs, or any laboratory or other assessments considered to be clinically relevant) will be collected at 24 hours post-dose or at any later time point at an unscheduled visits in the event of a safety signal being abnormal during the post-administration safety recordings or in the event of an AE.

### 7.3.2 Laboratory safety assessments

Please refer to Section 7.1.2 for laboratory safety assessments to be performed during the screening visit.

Day 1:

A urine pregnancy test (female subjects only), drug abuse test and breath alcohol test will be repeated before IMP administration.

During the IMP administration visit, sampling for the safety laboratory parameter set will be performed at baseline and at 90, 180 and 250 min post-injection (healthy volunteers) or at baseline, 45, 180 and 240 min post-injection (subjects with PCa). The safety laboratory parameter set will include all laboratory assessments described in Section 7.1.2, except for PSA, FSH, serum  $\beta$ hCG and the serology assessments.

Urine analysis will be performed at baseline and at 250 min post-injection (healthy volunteers) or at 240 min post-injection (subjects with PCa).

Day 2:

At the 24 hour follow-up visit, the safety laboratory parameter set will be repeated and will include all laboratory assessments described in Section 7.1.2, except for PSA, FSH, serum  $\beta$ hCG and the serology assessments.

The urine analysis will also be repeated.

Additional follow-up:

Additional laboratory safety assessments may be performed later as needed in the event of an AE or a safety variable being clinically significantly abnormal in the post-administration safety samples.

### 7.3.3 Adverse events

AEs will be collected throughout the study from informed consent onwards. During the study visits, the subjects are monitored for AEs and they are asked about AEs with non-leading questions. They are asked to report AEs immediately when they appear outside of the visit schedule. Outside of the visits, the subjects are to contact the study personnel in case of a significant AE, particularly in case of possibly IMP-related AEs. In case of minor AEs, the subjects are to report them on their next visit to the study site or during the scheduled telephone contacts. In case of any illness, the subjects are instructed to seek regular medical care and to inform the study site about their condition and possible changes in their medication as soon as possible.

Definitions of adverse events (AE) and serious adverse events (SAE) and the documentation and reporting of them within this study follow GCP, EU and Finnish national guidance.

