**Table 1** **General study outline**

	Screening (Day -21 to 0)	IMP administration visit (Day 1) a	24-hour follow-up visit (Day 2) b	30-day follow-up c
Informed consent	x			
Entry criteria	x			
Demography data	x			
Medical History	x			
Physical examination	x	x		
12 lead ECG	x	x	x	
Continuous ECG monitoring (lead II)		x		
Body weight	x	x		
Height	x			
Vital signs (supine BP and HR, body temperature, respiration rate) d	x	x	x	
Clinical laboratory tests	x e	x f	x f	
Urine analysis (stick test)	x	x	x	
Fertility status for female subjects	x			
Pregnancy test for female subjects		x		
Drug abuse test	x	x		
Alcohol breath test	x	x		
IMP administration		x		
PET-CT imaging		x		
Urine for  F radioactivity counting		x		
Venous blood for  F radioactivity counting and % radioactive parent analysis		x		
Injection site monitoring		x	x	
Concomitant medications	x	x	x	x
AEs and SAEs	x	x	x	x

a Please refer to Tables 2 and 3 for time points of activities to be performed during IMP administration visit.

b Visit will be performed 24 h (+/- 6 hours) after IMP administration.

c Subjects will be contacted by telephone at 30 days (+/- 2 days) after IMP administration and will be asked a non-leading question to determine whether any AEs have occurred. Extra study visits will be arranged as needed for AE management.

d Before vital signs are measured, the subject should be resting for at least 5 minutes.

e Please refer to Section 7.1.2 for laboratory safety assessments to be performed during the screening visit.

f The safety laboratory parameter set. Please refer to Section 7.3.2.

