## 10 ETHICAL CONSIDERATIONS

This study will follow the relevant regulations and guidance for biomedical research involving human subjects, such as the Declaration of Helsinki, GCP, and national and EU legislation. Special emphasis will be put on the well-being of the study subjects.

Prior to initiation of the study, the study protocol, the ICF, the Data Filing system (according to GDPR) and the text of any advertisements used for the recruitment of study subjects will be submitted to and approved by an independent EC. Additionally, the EC will be notified of any study materials to be given to the subjects (e.g. study subject diary, participant card). The study will be authorised by the CA (the Finnish Medicines Agency, Fimea) before its commencement.

The study subject candidates will be provided both verbal and written information on the study, its risks and benefits. Subjects are encouraged to ask questions on the study. After having had enough time to consider their participation, they may sign the ICF after a consent discussion, in the presence of the Investigator or his designee. No study procedure will be implemented prior to obtaining written informed consent. A copy of the signed ICF will be given to the subject. The Investigator keeps each subject's signed ICF on file.

The collection and processing of personal data from subjects enrolled in this study will be limited to those data that are necessary to fulfil the objectives of the study. These data must be collected and processed with adequate precautions to ensure confidentiality and compliance with applicable data privacy protection laws and regulations. Appropriate technical and organizational measures to protect the personal data against unauthorized disclosures or access, accidental or unlawful destruction, or accidental loss or alteration must be in place. Sponsor personnel whose responsibilities require access to personal data agree to keep the identity of subjects confidential.

The informed consent obtained from the subject includes explicit consent for the processing of personal data and for the Investigator/institution to allow direct access to his or her original medical records (source data/documents) for study-related monitoring, audit, IEC/IRB review, and regulatory inspection. This consent also addresses the transfer of the data to other entities and to other countries.

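### Protocol section 7.3.3 asks subjects both to report adverse events at once and to hold minor ones for the next contact, which after 24 hours is a single call at day 30

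*Protocol*

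**What the plan says.** Section 7.3.3 gives four instructions on events that arise between visits, one after another.

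- All events: "They are asked to report AEs immediately when they appear outside of the visit schedule". No severity limit is attached.
- Contact between visits: "Outside of the visits, the subjects are to contact the study personnel in case of a significant AE, particularly in case of possibly IMP-related AEs".
- Minor events: "In case of minor AEs, the subjects are to report them on their next visit to the study site", or else in scheduled telephone contacts, which the sentence puts in the plural.
- Any illness: subjects seek regular care and "inform the study site about their condition and possible changes in their medication as soon as possible".

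Section 10 adds that subjects are asked to report every AE to the study staff, and that they receive telephone numbers to use if they notice AEs.

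The contact schedule is in sections 3.3 and 6.3 and in Table 1. There is a visit at 24 hours (+/- 6 hours) and then one telephone contact at 30 days (+/- 2 days), with extra visits only where an AE needs managing. At the call the subject "will be asked a non-leading question to determine whether any AEs have occurred" (Table 1, footnote c).

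Section 2.3 makes the occurrence of treatment-emergent AEs, from injection throughout the study period, part of the primary endpoint. Section 7.3.3 requires all AEs to be recorded until participation ends, whether volunteered or elicited.

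**The concern.** A subject with a mild headache on day 5 cannot follow both the first and the third instruction. One says report now; the other says wait for the next contact. Waiting would matter little if contacts were frequent, but here the next contact is the end-of-study call. The plural in the deferral sentence suggests several telephone contacts, and the schedule contains one.

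The deferred class is not marginal. Section 7.3.3 defines the mild grade as an experience that is minor, so the deferral sentence covers in effect a whole severity grade. Section 8.2.7 summarises AEs by system organ class and preferred term, and also by seriousness, severity and relationship. If mild events after 24 hours are forgotten before the call, those tables understate them. Start and end date and time, which section 7.3.3 asks for as far as possible, are also harder to obtain weeks later. Sections 7.3.1 and 7.3.2 allow additional assessments in the event of an AE, and an event that has resolved before the call can no longer be examined while present.

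**Working it through.** The plan states no figure on this point, so there is nothing to reproduce. The check has three parts.

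**1. The instructions side by side, for a minor AE that starts between visits and is not an illness**

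| Source | What the subject should do |
|---|---|
| Section 7.3.3, immediate-reporting sentence | Report at once |
| Section 7.3.3, contact sentence | Contact called for only if the AE is significant |
| Section 7.3.3, deferral sentence | Wait for the next visit or call |
| Section 10 | Report all AEs; call when one is noticed |

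The first and last rows agree. The deferral sentence contradicts both. The contact sentence makes the subject judge significance first.

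**2. Longest recall under the deferral sentence**

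Inputs: visit at 24 h +/- 6 h, that is 18 to 30 h after injection; call at 30 +/- 2 days, that is day 28 to day 32 (sections 3.3 and 6.3). The gap is the time of the call minus the time of the visit.

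- Nominal: 30 - 24/24 = 29 days.
- Shortest: 28 - 30/24 = 28 - 1.25 = 26.75 days.
- Longest: 32 - 18/24 = 32 - 0.75 = 31.25 days.
- If the 2-day extension allowed in Cohort A for delayed surgery comes on top of the call window: 34 - 0.75 = 33.25 days.

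These are maxima, for an event that starts just after the 24-hour visit. An event starting on day t needs recall over about 30 - t days, for example 15 days for an onset on day 15.

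**3. What one missed event can change**

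Inputs: the planned evaluable numbers in section 4.2. The safety set holds all subjects given the product, so it may be somewhat larger and the steps below correspondingly smaller.

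The primary endpoint is worded as the occurrence of one or more treatment-emergent AEs. A forgotten event changes a subject's status only if it was that subject's sole such event. Where it was, the percentage moves by one subject:

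- all subjects: 1/15 = 6.7 percentage points;
- patients: 1/9 = 11.1 points;
- healthy volunteers: 1/6 = 16.7 points;
- a single patient cohort: 1/3 = 33.3 points.

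In the tables by preferred term and severity, a missed event can remove a subject from a cell even if that subject had other AEs.

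**The case against.** The strongest reply is that the sentences can be read as a general request followed by refinements: significant events and illnesses promptly, minor ones at the next contact. On that reading section 7.3.3 is coherent. But the deferral is then the operative rule for minor events, the gap of about 29 days applies in full, and the conflict with section 10 remains.

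The second reply concerns scope, and it stands. AEs up to 24 hours are collected by direct monitoring and questioning. Significant AEs and any illness are to be notified without waiting. Laboratory tests, ECG, vital signs and injection-site findings do not rest on memory. The interval after 24 hours is 29 of 30 days, or 97 % of calendar time, but that is not 97 % of the risk. The product is given once, and with the 110-minute half-life in section 1.1, 24 h is 1440/110 = 13.1 physical half-lives. The study is exploratory (section 8.2.2), and no stated decision turns on the count of late mild events.

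Three stronger readings are tempting, and the protocol does not support them.

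- **The whole primary endpoint depends on a month's recall.** It does not. Only minor AEs starting after the 24-hour visit do, and only in subjects who follow the deferral sentence.
- **The share of AEs called related is biased upwards, because subjects are told to call particularly about events they link to the product.** The trigger for contact is a significant AE; the link to the product is an added emphasis. Events not telephoned in are still asked about at day 30, all AEs are recorded, and the Investigator assigns causality. The clause can affect when an event is reported. A shift in the related share is not shown.
- **A definite fraction of late mild events is lost.** The protocol holds no recall rate, so any such percentage would only restate an assumption.

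Nor does a diary already close the gap. Section 10 names a "study subject diary" only as an example of material that might be given to subjects, and no schedule or assessment section uses one.

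**Conclusion.** The inconsistency is real and lies in the protocol's own text: the deferral sentence in section 7.3.3 conflicts with the immediate-reporting sentence in the same section and with section 10. Its consequence is narrow. Minor treatment-emergent AEs that start after 24 hours may be captured only by recall over up to about 29 days (26.75 to 31.25 within the stated windows), although sections 2.3 and 7.3.3 call for all of them. The likely direction is an under-count of late mild events; its size cannot be derived from the protocol. The conclusion assumes that some subjects follow the deferral sentence, and that some minor events are forgotten before the call. It is worth correcting because safety is the primary endpoint, the groups are small and the correction is nearly free.

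**What to change.** - In section 7.3.3, delete the sentence that defers minor AEs and the clause that stresses possibly product-related events.
- State one rule, in the same words in sections 7.3.3 and 10: subjects report all AEs when they occur, whatever their severity or presumed cause.
- Replace the plural telephone contacts in section 7.3.3 with the single 30-day call.
- Optionally, give each subject a one-page dated note sheet for AEs, to be read through at the existing call. This would be a new item. No visit is scheduled after the 24-hour one, so the amendment would have to say how the sheet is returned or transcribed. The contradiction is cured without it.

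The cost is a short wording amendment and matching instructions to subjects, with no extra visit or scheduled call. The downside is a few more unscheduled calls to the site and slightly higher reported counts of mild AEs.

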#### Adverse Events

An AE is defined as any untoward medical occurrence experienced by a subject, whether or not considered related to IMP administration by the Investigator. For the current study, all AEs will be coded using the Medical Dictionary for Regulatory Activities (MedDRA, version 21.0 or later) by the data management (DM) provider in co-operation with CRST.

AEs are:

- Unfavourable changes in general condition.
- Subjective or objective signs/symptoms.
- Concomitant diseases or accidents.
- Clinically relevant adverse changes in laboratory parameters observed in a subject in the course of a clinical study.

AEs comprise all disturbances of general health status, subjective and objective disease symptoms (including significant, clinically relevant laboratory abnormalities), concomitant diseases, and accidents observed in the context of a clinical trial, irrespective of a possible causal relationship with IMP administration.

All AEs, whether volunteered, elicited, or noted on physical examination, will be recorded throughout the study, i.e., from the screening visit until the end of the subject's participation. AEs that occur prior to IMP administration will be reported separately from treatment-emergent AEs, which will be of particular interest.

When an AE occurs, the first decision will be to determine its severity and relationship to the IMP.

The severity of AEs will be categorised as follows:

- Mild = Experience is minor and does not cause significant discomfort to subject or change in activities of daily living (ADL) compared to subject baseline; subject is aware of symptoms but symptoms are easily tolerated.
- Moderate = Experience is an inconvenience or concern to the subject and causes interference with ADL compared to subject baseline but the subject is able to continue with ADL.
- Severe = Experience significantly interferes with ADL and the subject is incapacitated and/or unable to continue with ADL compared to subject's baseline.

The relationship of an AE to IMP administration will be categorised as follows:

- Related; when there is a reasonable possibility of a causal relationship between IMP administration and an AE (i.e. adverse drug reaction, ADR)
- Not related; when an AE does not follow a reasonable temporal sequence from IMP administration or when an AE can be reasonably explained by other factors including underlying disease, concomitant drugs or concurrent treatment.
- Not applicable: IMP not administered or AE is prior to IMP administration.

The Investigator or his delegate marks on the AE-CRF all AEs, indicating the Investigator's assessment of a causal relationship to IMP administration using the categories above.

As far as possible, each AE will also be described by its duration (start and end date and time), the actions taken, and, as relevant, the outcome.

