#### 4.10 Evaluability criteria and additional subjects

Healthy Volunteer Evaluability Criteria:

As it is important that the study has the required number of evaluable healthy volunteers, the following criteria will be applied, and if the healthy volunteer is not evaluable for efficacy, an additional subject may be included in the study to substitute for the non-evaluable subject:

- Completion of scanning sessions I, II and III and collection of venous blood and urine analysis (as described in the Study Imaging Manual) to be able to undertake a calculation of the subject's internal radiation dosimetry.

Patient Evaluability Criteria:

As it is important that each cohort has the required number of evaluable patients, the following criteria will be applied and if the patient is not evaluable for efficacy, an additional subject may be included in the study to substitute for the non-evaluable subject:

- Completion of scanning sessions I and II and collection of venous blood and urine analysis (as described in the Study Imaging Manual) to be able to perform kinetic modelling.
- At least one positive lesion on the F-rhPSMA-7.3 scan.
- Cohort A only: Radical prostatectomy performed within 30 days of the F-rhPSMA-7.3 scan. In case of a delay of the planned surgery by up to 2 days beyond this 30-day window, a subject may still be considered evaluable.

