### Suspected Unexpected Serious Adverse Reactions

An unexpected adverse drug reaction is any serious adverse drug reaction (ADR), the nature or severity of which is not consistent with the approved Reference Safety Information contained within the current Investigator's Brochure (IB) of F-rhPSMA-7.3. Suspected unexpected serious ADRs (SUSARs) are subject to expedited reporting to the CA. The PV provider reports all authority-reportable AEs to the Sponsor and the CA.

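### The two causality categories in Protocol section 7.3.3 overlap and no rule says which prevails, so an AE that the tracer may reasonably have caused can be recorded as not related (minor)

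*Protocol*

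**What the plan says.** Protocol section 7.3.3, under Adverse Events, gives three relationship categories.

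- *Related* applies "when there is a reasonable possibility of a causal relationship between IMP administration and an AE (i.e. adverse drug reaction, ADR"). The category is thus equated with an ADR.
- *Not related* applies in either of two situations joined by *or*. The first concerns timing: "when an AE does not follow a reasonable temporal sequence from IMP administration". The second concerns a competing cause, and applies "when an AE can be reasonably explained by other factors including underlying disease, concomitant drugs or concurrent treatment".
- The third is "Not applicable: IMP not administered or AE is prior to IMP administration".

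The investigator or a delegate records each AE, "indicating the Investigator's assessment of a causal relationship to IMP administration using the categories above". No order of precedence between the categories is given there or in the SAE and SUSAR text that follows.

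The judgement is used in four places:

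- Section 8.2.7 summarises AEs by relationship.
- Section 7.3.3 makes SUSAR status depend on an event being an ADR: "Suspected unexpected serious ADRs (SUSARs) are subject to expedited reporting to the CA".
- Section 7.3.3 exempts admission for prostate cancer treatment from SAE status, unless (among other conditions) the investigator judges it caused by the IMP.
- Section 13 words one example of a reason for early termination in terms of ADRs.

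**The concern.** A two-level scale works only if each post-dose AE belongs to one level. Here the levels are not complements. One asks whether the tracer is a reasonable possibility, and the other can be met by asking whether something else is a reasonable explanation. Both answers can be yes for the same event.

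Followed literally, the text lets an investigator record *Not related* while a reasonable possibility of causation remains. The event would then be missing from the related-AE rows and would not count as an ADR. If it were serious and unexpected, it would fall outside the protocol's definition of a SUSAR.

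The judgement is made when the AE is recorded. A later analysis plan cannot recover it, so this is not a detail that the SAP could settle.

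**Working it through.** The protocol has no figure of its own to reproduce here. The check is a logical comparison of the definitions, followed by the size of one reclassification.

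**Step 1: definitions side by side.** Let R = the tracer is a reasonable possible cause. Let N = (timing does not fit) OR (another factor reasonably explains the AE). The categories are exclusive only if R and N cannot both be true, or if a tie-break is stated.

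| Timing fits | Another reasonable explanation | Tracer a reasonable possibility | Meets *Related* | Meets *Not related* |
|---|---|---|---|---|
| No | Yes or no | No | No | Yes |
| Yes | No | Yes | Yes | No |
| Yes | Yes, leaving no reasonable role for the tracer | No | No | Yes |
| Yes | Yes, but the tracer remains reasonable | Yes | **Yes** | **Yes** |

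The last row is the overlap. The third category does not resolve it, because it covers only AEs before dosing or without dosing.

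**Step 2: can the last row occur?** Competing explanations are built into the patient groups. All patients have prostate cancer (section 4.5). Section 4.10 requires "Cohort A only: Radical prostatectomy performed within 30 days of the" scan, with up to 2 days' tolerance, so surgery falls largely within AE follow-up. Cohort C has ongoing androgen deprivation or orchiectomy (section 4.5). Cohorts A and B exclude current or past hormonal treatment (section 4.6), so that explanation applies to Cohort C only. As an illustration, nausea soon after injection in a Cohort C patient, which his ongoing treatment could also reasonably explain, meets both definitions. Healthy volunteers can fall in the overlap too, but have fewer competing causes.

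**Step 3: size of one reclassification.** Planned evaluable numbers are from section 8.1. The shift in the percentage of subjects with a related AE is 1/n, provided that the AE is that subject's only related one.

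- One patient cohort: 1/3 = 33.3 percentage points
- All patients: 1/9 = 11.1 points
- All subjects: 1/15 = 6.7 points

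The safety set holds everyone dosed (section 8.2.3), so replacement subjects would make these shifts smaller. For example, with one replacement in a cohort the shift is 1/4 = 25.0 points.

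**Step 4: what does not depend on the category.** The primary endpoint (section 2.3) uses treatment-emergent AEs whatever their cause, together with changes in laboratory and clinical measures. The 24-hour SAE report to the pharmacovigilance provider (section 7.3.3) is also made whatever the cause.

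**The case against.** The strongest reply is that the bullets describe a single clinical judgement: either the tracer is a reasonable possibility, or timing or another cause accounts for the event better. A careful investigator may well read them so. Several further points also stand.

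- **Direction.** A reader might infer a one-way bias toward fewer related events. The text does not show that: an AE that meets both definitions may equally be recorded as *Related*.
- **Threshold.** The competing cause must reasonably explain the event. A merely conceivable one is not enough, which narrows the overlap without removing it.
- **Primary endpoint.** A reader might infer that the primary safety result is distorted. It does not use causality.
- **Group comparison.** A reader might infer that related-AE rates in patients and volunteers are being compared on different scales. The protocol states no hypotheses (section 8.2.2), and its analysis is exploratory and descriptive (section 8.2.4).
- **Safeguards.** Serious events reach the pharmacovigilance provider whichever category is chosen. Section 7.3.3 places AE documentation and reporting under GCP, EU and Finnish guidance. Subject listings let a reader inspect events singly in a study of about 15 people.

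These points limit the consequence. They do not remove the defect. The words as printed do not say that the other cause must be the better explanation, the general reference to guidance does not say how to choose between two categories that the protocol itself defines, and listings carry the recorded category, not the one that a clearer rule would have produced.

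**Conclusion.** The categories *Related* and *Not related* are not mutually exclusive, and no precedence rule is given. The text therefore permits *Not related* for an AE that the tracer may reasonably have caused. The possible effect is confined to the tables by relationship, ADR and SUSAR classification, the exemption for prostate cancer hospitalisation, and ADR-based termination judgements.

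Severity is minor. The percentages above are the size of a single reclassification, not an expected error, since the documents give no basis for estimating how often the overlap would arise or how investigators would resolve it. The conclusion rests on reading the *or* literally. For the hospitalisation exemption, it also assumes that the investigator applies the same causality standard there as on the AE form.

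**What to change.** In section 7.3.3, redefine *Not related* as the complement of *Related*: no reasonable possibility that the IMP caused or contributed to the AE, for example because the timing does not fit, or because another cause leaves no reasonable role for the IMP. Then add a sentence such as: *An AE that meets both descriptions is classified as Related, even if another factor could also explain it.* Use the same text in the eCRF completion guidance.

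The cost is a short wording change in the protocol and the eCRF guidance. The two-level scale, the assessments, the tables and the reporting route stay as they are. The downside is that a few more AEs may be labelled related.
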